PROTOCOL

PROTOCOL TITLE	A prospective randomized trial of antibiotic duration in post-appendectomy abscess
PROTOCOL NUMBER	17-055
STUDY DESIGN (PHASE)	Prospective randomized
PROTOCOL VERSION	Version 5 Dated September 25, 2019
NCT NUMBER	NCT03795194
SPONSOR	[name] Phoenix Children's Hospital [name]
PRINCIPAL INVESTIGATOR	[name]

IRB#: 17-055

Title: A prospective randomized trial of antibiotic duration in post-appendectomy abscess

PI: [name]

Col's: [name], [name]; [name]; [name]; [name]; [name]; [name]; [name] [name]; [name]; [name].

Abstract

Appendicitis is a very common surgical problem in children. Although the rates of post-appendectomy abscess in simple appendicitis are less than 1%, the rates of post-appendectomy abscess in complicated appendicitis are not well-described.⁵⁻⁸ Complicated appendicitis includes patients who present with a visible perforation and/or feces in the abdomen, a primary abscess, phlegmon, gangrene, or all of the above.²⁻⁴ Research suggests that neither the type of the antibiotic therapy nor duration of treatment has a significant impact on reducing the risk of post-operative abscess for patients who present with any form of complicated appendicitis.⁷ However, the lack of an evidence-based definition of perforated appendicitis has undermined the reliability of most research results because the study populations may have included non-complicated patients. In this study, we propose to assess the equivalence of an 8-day fixed course and a fixed 4-day course of antibiotics at drainage for perforated patients who develop a post-surgical abscess. We are proposing to study 342 pediatric patients (includes 10% oversampled) ages 2 to 17 years at institutions in the Western Surgical Pediatric Research Consortium (WSPRC) who are diagnosed with perforated appendicitis, treated laparoscopically, **and form an abscess post-laparoscopy**. We hypothesize that the 8-day course of antibiotics is equivalent to the 4-day course on the primary clinical outcome (i.e., readmission rate) and secondary outcomes: length of stay (LOS) upon readmission; rate of abscess from drainage until 30 days after discharge, and wound infection from drainage until 30 days of discharge. This research will provide an ongoing contribution to the clinical management of complicated pediatric appendicitis and antibiotic stewardship.

A. Introduction/Background

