The central hypothesis tested in this study is whether a 4-day antibiotics course is equivalent to an 8-day course for post-drainage primary and secondary clinical outcomes.

Primary outcomes:

- readmission rate

Secondary Outcomes:

- length of stay (LOS)
- rate of post-drainage surgical site infection until 30 days after discharge
- rate of post-drainage abdominal abscess until 30 days after discharge
- secondary site infections

C. Methods

C.1. Study Design

This research proposes a randomized, prospective, equivalence trial design to test the research hypothesis. This study will demonstrate no difference in clinical outcomes between the 4-day antibiotic course and the 8-day course. The study will include 342

IRB#: 17-055

Title: A prospective randomized trial of antibiotic duration in post-appendectomy abscess

PI: [name]

Col's: [name], [name]; [name]; [name]; [name]; [name]; [name]; [name] [name]; [name]; [name].

pediatric patients (includes 10% oversampled) ages 2 through 17 years treated from February 1, 2019 onward until the study cohorts have been filled. This study is based on an expectation of 90% success (10% readmitted) in arm A=10% and expectation of 90% success (10% readmitted) in arm B =10%. The clinical difference in primary outcome between the two groups that we are prepared to accept is equal or greater than 10% (i.e., clinically, we are willing to accept 10 children per 100 who may have benefited from the long course but received a short course to achieve 90% of children who received the short course and would not have benefitted from a long course). The sample size needed to attain a power of 0.80 at alpha=0.05 is 342 (171 in each arm, which includes a 10% attrition rate). The risk of type I error is 1-0.95 (alpha=0.05); power=0.80. The study will proceed until 171 patients are consented for each arm. Study personnel will perform an interim analysis of the data approximately halfway through study enrollment.

Definition of perforated appendicitis - Perforated appendicitis is defined as a visible hole or feces found in the abdomen at laparoscopy. ***For purposes of research, either the hole or feces is photographed, and "hole," "feces/stool in the abdomen," or other note describing perforation will need to be specifically described in the operative report.***

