Col's: [name], [name]; [name]; [name]; [name]; [name]; [name]; [name] [name]; [name]; [name].

It is estimated that it will take about 6 years for PCH to fill the study arms; interim analysis will be performed when study cohorts are half-filled. In order to complete this and other planned pediatric appendicitis studies more quickly, we are planning to add other study sites through the Western Surgical Research Consortium. The multisite approval process will be facilitated by Streamlined Multisite Accelerated Resources for Trials (SMART) IRB certification. With participation from the nine hospitals in the Western Surgical Research Consortium, we would expect to fill the trial cohorts in approximately 2 years.

C.4. Data Analysis Plan

The study will describe patient and clinical characteristics related to laparoscopy among study cohorts (e.g., age, BMI, gender, maximum temperature upon admission, diarrhea at presentation, duration of symptoms, and white blood cell count); patient recovery and abscess formation (e.g., time to abscess, abscess size if available, time to regular diet, and LOS after the drainage); primary clinical outcome (readmission); and secondary clinical outcomes (LOS, total visits after discharge, post-drainage occurrence of abscess, and post-drainage secondary infection).

All data will be described using descriptive statistics, including means, standard deviation, and proportions. Differences among treatment cohorts and on clinical outcomes will be assessed using parametric and non-parametric tests as appropriate. Factors confounding outcomes will be identified *a priori* from research and empirically via correlational analysis for continuous measures or through non-parametric techniques for discrete variables with a Bonferroni correction for multiple comparisons among families of statistical tests. Binomial logistical regression will also be used where appropriate. Unadjusted odds ratios will be used to identify variables of interest and confounding effects for discrete dependent variables of interest. Adjusted odds ratios will be used to compare differences among study cohorts and covariates (e.g., age, gender, white blood cell count, and BMI), interactions, and confounders as appropriate. Statistical significance will be defined as an alpha of 0.05, with two-sided alternative hypothesis and a Bonferroni correction for multiple comparison. Data analysis will be performed using SPSS and R.

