There will be no direct patient benefit from this study. This research will benefit clinical management by evaluating whether patients achieve significant differences in primary and secondary clinical outcomes based on duration of antibiotic treatment at abscess drainage. The study results may help lower costs for post-appendectomy patient care, improve infection management, and contribute to antibiotic stewardship.

E. Confidentiality and Protection of Human Subjects

E.1. Data Protection, Privacy, Storage, and Security

In accordance with standards for human subjects review, the research study team will adhere to precautions to protect participant privacy and confidentiality of information. Trauma Research will hold the master key of participant names and unique identifiers for use in tracking cases, connecting to data from electronic health records (EHRs), and de-identifying data. All data will be collected by Trauma Research, de-identified, and entered into an encrypted, cloud-based, HIPAA-compliant server (REDCap). Trauma Research will access the data through the website and download to a secure, password-protected network drive at PCH for storage and analysis.

Identifiable patient information will be retained only for as long as the data can be cleaned, verified, and prepped for data analysis. De-identified data will be maintained for up to three months after acceptance of the first scholarly journal article or until study closure, whichever comes first. For data identified for disposal, appropriate measures will be taken; electronic data will be deleted from office computers and the primary location of storage in the network drive, and hard copies containing data will be shredded and disposed of in accordance with PCH policy.

IRB#: 17-055

Title: A prospective randomized trial of antibiotic duration in post-appendectomy abscess

PI: [name]

Col's: [name], [name]; [name]; [name]; [name]; [name]; [name]; [name] [name]; [name]; [name].

E.2. Standard of Care, Confidentiality, and Privacy

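### C.1 sizes an equivalence trial on a 10-point margin, but C.4 plans only difference tests and gives no rule for concluding equivalence

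*Combined protocol and SAP*

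**What the plan says.** The equivalence aim appears in three places.

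- **Abstract:** "We hypothesize that the 8-day course of antibiotics is equivalent to the 4-day course on the primary clinical outcome", and the same sentence goes on to the secondary outcomes.
- **Section B:** the central hypothesis is "whether a 4-day antibiotics course is equivalent to an 8-day course for post-drainage primary and secondary clinical outcomes".
- **Section C.1:** the design is named as an equivalence trial, and "This study will demonstrate no difference in clinical outcomes between the 4-day antibiotic course and the 8-day course".

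C.1 also gives the sizing inputs: 10% readmitted in each arm, alpha 0.05, power 0.80, and 171 per arm (342 in total) including 10% attrition. The limit is worded "The clinical difference in primary outcome between the two groups that we are prepared to accept is equal or greater than 10" (per cent) and explained as "clinically, we are willing to accept 10 children per 100 who may have benefited from the long course but received a short course".

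Section C.4 covers descriptive statistics, tests of differences ("Differences among treatment cohorts and on clinical outcomes will be assessed using parametric and non-parametric tests as appropriate"), screening for confounders, logistic regression, and unadjusted and adjusted odds ratios. Its decision standard is "Statistical significance will be defined as an alpha of 0.05, with two-sided alternative hypothesis and a Bonferroni correction for multiple comparison". It mentions neither the 10-point limit, nor a confidence interval for the risk difference, nor an equivalence test.

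Section D.2 describes the value of the study as "evaluating whether patients achieve significant differences in primary and secondary clinical outcomes based on duration of antibiotic treatment at abscess drainage".

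**The concern.** A difference test takes no difference as its null hypothesis, so failing to reject it shows nothing about how large the difference might be. An equivalence claim reverses the hypotheses: the null is a difference of at least the margin, and the data must reject it. C.1 is built on the second logic and C.4 on the first.

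No sentence says that p > 0.05 means equivalence. But C.1 promises to show no difference, D.2 asks about significant differences, and C.4 offers no other criterion, so a non-significant result could easily be reported that way. Under that reading, the chance of wrongly calling the short course equivalent is uncontrolled and grows as the evaluable sample shrinks. Bonferroni, which guards against false claims of difference, would make it larger still.

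Decisions hang on this. Section D.1 has the investigators judge whether interim results support closing, completing or extending the trial, and mentions a possible no-antibiotic arm if the study succeeds. Success is not defined.

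Two lesser points belong with it. The secondary outcomes also carry equivalence hypotheses but have no margins. And C.1's wording of the limit is literally reversed, although the per-100-children explanation shows that 10 points was meant as the most that would be accepted.

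**Working it through.** **Inputs.** From C.1: readmission 10% in both arms, limit 10 percentage points, alpha 0.05, power 0.80, 10% attrition, 1:1 allocation. From C.4: two-sided 0.05, Bonferroni with no stated number of comparisons.

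**Step 1: reproduce 342.** For two one-sided tests with a true difference of zero:

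n per arm = 2p(1 − p)(z₀.₉₅ + z₀.₉₀)² / margin² = 2 × 0.1 × 0.9 × (1.645 + 1.282)² / 0.10² = 154.1 (unrounded quantiles), so 155.

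155 × 1.1 = 170.5, so 171 per arm and 342 in total. This matches the protocol.

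**Step 2: evaluable patients.** After 10% attrition, 171 × 0.9 = 153.9, about 154 per arm.

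**Step 3: compare the two decision rules.** Exact enumeration of two independent binomials, with the 8-day arm at 10%. The difference test is the pooled z-test (uncorrected chi-square) at two-sided 0.05. Equivalence means that the 90% Wald interval for the risk difference lies inside ±10 points.

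| Evaluable per arm | True readmission, 8-day vs 4-day | Difference test non-significant | Equivalence shown |
|---|---|---|---|
| 154 | 10% vs 20% | 30.1% | 5.3% |
| 171 | 10% vs 20% | 25.4% | 5.4% |
| 77 | 10% vs 20% | 57.8% | 2.6% |
| 154 | 10% vs 15% | 73.6% | 37.3% |
| 154 | 10% vs 10% | 95.0% | 79.4% |

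The 77 is half of 154 and only illustrates a smaller evaluable sample. With less data, the non-significance rule passes more trials at the margin and the equivalence rule passes fewer. When the arms truly have the same rate, 15.6% of trials at 154 per arm are non-significant without showing equivalence.

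**Step 4: Bonferroni.** If it applied to the primary test, the 30.1% would become 41.2%, 46.8%, 51.1% and 54.8% for assumed divisors of 2, 3, 4 and 5.

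**Step 5: a worked result.** Readmissions of 15/154 (8-day) and 26/154 (4-day) differ by 11/154 = 7.1 points.

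- Pooled z = 1.85, p = 0.065, not significant.
- Standard error 3.85 points; 90% interval 7.14 ± 1.645 × 3.85 = +0.8 to +13.5 points. A difference beyond 10 points is not excluded, so equivalence is not shown.

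The difference test is not blind to everything: 15/154 against 30/154 gives p = 0.016.

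**Step 6: scale.** At a 10% base rate, the 10-point limit is an odds ratio of (0.20/0.80) / (0.10/0.90) = 2.25. The odds ratios in C.4 are therefore not on the scale of the margin, and C.4 gives no translation.

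**The case against.** - **The phrase about tests as appropriate could cover an equivalence test.** The subject of that sentence is differences, the significance standard is two-sided with no exception for the primary outcome, and the margin is absent. A test left unnamed is not pre-specified.
- **The sample size does not by itself prove that two one-sided tests were meant.** This stands. A one-sided difference test of 10% against 20% with unpooled variance gives (1.645 + 0.842)² × (0.09 + 0.16) / 0.10² = 154.6, also 155 and so 171 per arm. The arithmetic is consistent with two one-sided tests; the named equivalence design and the equal 10% rates are what favour them.
- **The 30% rests on a rule that the protocol does not state, and on full attrition.** Both parts are true. It measures one plausible misuse. Section C.1 expects little loss to follow-up in its follow-up paragraph, and with all 171 evaluable the figure is 25%. The missing rule does not depend on either number.
- **The Bonferroni range is speculative.** With one primary outcome and two arms, a divisor of 1 is a natural reading. But C.4 does not say so, and it should.
- **The interval could be computed from the data anyway.** It could. What is missing is the commitment, made before the data are seen, to judge it against the margin.
- **The power depends on the interval method and level.** This stands. A Newcombe 90% interval gives 77.7% at 154 and 78.9% at 155 per arm, slightly below the Wald figures, so the method should be named.

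**Conclusion.** The concern holds and must be fixed. C.1 sets up an equivalence trial with a 10-point limit, and C.4 contains no analysis that uses the limit and no criterion for declaring equivalence. As written, the planned analysis does not answer the central hypothesis.

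If non-significance were taken as equivalence, a true 10-point excess in readmission would be called equivalent in 25% to 30% of trials (171 to 154 evaluable per arm), against about 5% with two one-sided tests. These figures assume 10% readmission on 8 days, an uncorrected chi-square test without Bonferroni, and a limit of 10 absolute percentage points. The sample size itself is not in question.

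**What to change.** **In C.4, add a primary analysis paragraph**, for example:

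> The primary analysis is the risk difference in readmission (4-day minus 8-day) with a 90% confidence interval, corresponding to two one-sided tests each at 0.05. Equivalence is concluded only if the whole interval lies within -10 to +10 percentage points. A non-significant difference test is not evidence of equivalence.

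Name the interval method and the analysis population in the same paragraph.

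**In C.4, open the significance sentence** with an exception for the primary equivalence analysis, so that neither the two-sided alternative nor Bonferroni applies to it.

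**In C.1**, state the acceptable difference as less than 10 percentage points, and replace the promise to show no difference with an aim to test equivalence in readmission.

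**In the Abstract and Section B**, limit the equivalence hypothesis to readmission and report secondary outcomes as estimates with confidence intervals. The alternative is to pre-specify a margin for each.

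**Cost.** Protocol wording only. With 90% Wald limits and no Bonferroni, exact power at 10% in both arms is 79.4%, 80.5% and 85.1% with 154, 155 and 171 evaluable per arm, so 342 can stay. The level is the sponsor's decision, but it has a price: at 154 per arm, 95% limits give about 67% power, and Bonferroni for an assumed four comparisons about 51%.

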Two arms are proposed for the study following the protocol implemented for adults in a recent randomized trial.²¹ In the control arm, patients will be treated with an 8-day course of antibiotics, and in the experimental arm, patients will be treated with a 4-day course of antibiotics. The randomized trial should control for all confounding effects. In addition,

IRB#: 17-055

Title: A prospective randomized trial of antibiotic duration in post-appendectomy abscess

PI: [name]

CoI's: [name], [name]; [name]; [name]; [name]; [name]; [name]; [name] [name]; [name]; [name].

we will collect clinical data on the pre-operative, peri-operative and post-operative antibiotic treatment and number of days on antibiotic therapy prior to discharge to manage this potential confounder *post hoc*.

There is a low probability of study attrition or loss to follow-up. As the primary treatment provider in a study with a short (30-day) follow-up period for readmission, we do not expect significant attrition. Follow-up will entail tracking all patients from the initial study who return to the hospital for complications related to the procedure within 30 days of discharge. All complications, including those requiring readmission, will be included in the follow-up. All study patients will be assessed for primary and secondary clinical outcomes. Complications associated with surgically treated acute appendicitis based on the National Surgery Quality Improvement Program criteria (available at <http://nsqip.healthsoftonline.com/hsi/>) include (1) wound infection, (2) abscess, (3) post-discharge small bowel obstruction, (4) hernia, (5) length of hospital stay of greater than 4 days, and (6) death.

[figure not shown]
IRB#: 17-055

Title: A prospective randomized trial of antibiotic duration in post-appendectomy abscess

PI: [name]

CoI's: [name], [name]; [name]; [name]; [name]; [name]; [name]; [name] [name]; [name]; [name].

Diagram 1: Treatment arms for randomized trial of an 8-day antibiotic treatment vs. 4-day treatment of post-laparoscopic abscess formation in pediatric complicated (perforated) appendicitis.

* If febrile after assigned course of antibiotics (i.e., 8 days or 4 days) is completed, extended antibiotic treatment will be up to the treating surgeon.

†Patient may be discharged before 8- or 4-day course is completed and may finish antibiotics at home.

IRB#: 17-055

V5 9/25/2019

IRB#: 17-055

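### Section C.4 names no main analysis of readmission and allows the arm comparison to be an adjusted odds ratio with outcome-selected covariates and interactions, which does not estimate the 10-point difference that sizes the trial

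*Combined protocol and SAP*

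**What the plan says.** Section C.1 describes an equivalence trial and sizes it on readmission proportions: 10% expected in each arm, an accepted difference of 10 percentage points, and 342 children (171 per arm) with 10% attrition included. It adds: "The risk of type I error is 1-0.95 (alpha=0.05); power=0.80".

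Section C.4 is the only analysis plan. It offers two routes to an arm comparison and does not rank them:

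- tests, parametric or otherwise, to be chosen as suits the data;
- logistic regression where suitable, with "Adjusted odds ratios will be used to compare differences among study cohorts and covariates (e.g., age, gender, white blood cell count, and BMI), interactions". The sentence goes on to add confounders and ends with a qualifier that leaves these terms to judgement.

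Confounders are to come from the literature and also from the trial's own data: "Unadjusted odds ratios will be used to identify variables of interest and confounding effects for discrete dependent variables of interest". On significance: "Statistical significance will be defined as an alpha of 0.05, with two-sided alternative hypothesis and a Bonferroni correction for multiple comparison".

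On confounding, C.1 says "The randomized trial should control for all confounding effects". It then adds that the length of antibiotic treatment before discharge will be recorded so that this possible confounder can be dealt with after the fact.

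**The concern.** This is an observational workflow applied to a randomised comparison. Four things follow.

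1. No result is named as the main one. Covariates, interactions, coding and the arm contrast to be reported can all be settled after outcomes are known.
2. The scale does not match the design. The margin is a difference in proportions; an odds ratio, adjusted or not, does not test it. An adjusted odds ratio is also conditional on its covariates, so it is not the average effect in the trial population.
3. If arm-by-covariate interactions are fitted, the arm coefficient is the effect at covariate value zero. On raw scales that means age 0 and BMI 0, while C.2 admits children from 2 through 17.
4. Randomisation follows drainage. Antibiotic days accrued after it can depend on the assigned course, so adjusting for them could remove part of the effect under study.

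At stake is whether the equivalence conclusion rests on one prespecified estimate or on the choice among several.

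**Working it through.** **Inputs from the documents.** "expectation of 90% success (10% readmitted) in arm A=10"% and "expectation of 90% success (10% readmitted) in arm B =10"%; 10-point margin; alpha 0.05; power 0.80; 171 per arm including 10% attrition (all C.1). Age 2 through 17 (C.2). The documents give no covariate means or SDs, so those below are assumptions.

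**The plan's own sample size.** Two one-sided tests at 0.05:
n = 2 × 0.1 × 0.9 × (1.645 + 1.282)² / 0.10² = 154.1, so 155 per arm. 155 × 1.10 = 170.5, so 171 per arm and 342 in total. The stated figure is reproduced, on the risk-difference scale.

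**Events.** 2 × 155 × 0.10 = 31 readmissions (34 if all 342 are followed). As an illustration, arm + 4 covariates + 4 arm interactions is 9 terms: 31/9 = 3.4 events per term, before any screened variable.

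**Scale.** Ten points correspond to different odds ratios at different base rates:
- 5% to 15%: (0.15/0.85)/(0.05/0.95) = 3.35
- 10% to 20%: (0.20/0.80)/(0.10/0.90) = 2.25
- 15% to 25%: (0.25/0.75)/(0.15/0.85) = 1.89

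**Standard error without adjustment.** SE of the arm log odds ratio = √(2/(155 × 0.1 × 0.9)) = 0.38.

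**Choice between models (simulation 1).** 1,500 trials per scenario, 155 per arm, ten standard-normal covariates with log odds ratio 0.25 each, four forced in and six screened on the outcome at p<0.05.

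| Model | Median SE, 10% v 10% | Power to detect 10% v 20% |
|---|---|---|
| Unadjusted | 0.38 | 69% |
| Adjusted, no interactions | 0.40 | 69% |
| Interactions, centred | 0.47 (true SD 0.52) | 64% |
| Interactions, means 2 SD from zero | 1.9 | 9% |

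With no difference, at least one of the first three models was significant in 7.5% of trials (simulation error √(0.075 × 0.925/1500) = 0.7 points). A repeat run gave 7%, with median SEs of 0.40, 0.42, 0.50 (true SD 0.57) and 2.0. Outcome screening alone gave a type I error of 4.5%.

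**Interactions on natural scales (formula and simulation 2).** The inflation from uncentred arm-by-covariate terms is about √(1 + Σ(mean/SD)²).
- Age only, uniform over 2 to 17: mean 9.5, SD 15/√12 = 4.33; √(1 + 4.81) = 2.4.
- Age only, mean 10, SD 4: √(1 + 6.25) = 2.7.
- All four (age 10, SD 4; 60% one sex, SD 0.49; WBC 15, SD 5; BMI 19, SD 4.5): √(1 + 6.25 + 1.50 + 9.00 + 17.83) = 6.0. Wider SDs (4.3, 7 and 6 for age, WBC and BMI) give 4.8. Narrower ones (3.5, 5 and 3.5, with WBC mean 17) give 7.2.

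Simulated logistic fits (310 children, 10% readmitted in both arms, 400 to 600 runs per setting) gave these ratios to the unadjusted SE:
- main effects only: 1.01
- all four interactions, centred: 1.1
- arm-by-age alone, uncentred: 2.8 to 3.2
- all four, uncentred: 4.8 to 7.5

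Simulation 1 gives 0.47/0.38 = 1.24 for centred interactions, hence a range of 1.1 to 1.3. There the reported SE is about 10% too small (0.47 against 0.52). In simulation 2 the empirical SD with centring was 0.57 to 1.08 against a median reported SE of about 0.43, driven by a few unstable fits.

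**The case against.** **C.4 permits this model and does not require it.** The text also lists unadjusted tests, gives the four covariates only as examples, names no interaction and does not say that any involves arm. This stands: the nine-term model above is an illustration, not the plan.

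**Centring is a reparametrisation.** It leaves the fitted risks unchanged. A reader might infer from the fivefold SE or the 9% power that the trial would lose most of its information. The documents do not support that. Those figures describe a coefficient read at covariate value zero, they need all four interactions uncentred and assumed means and SDs, and the average effect can be recovered from the same fit. Moreover, 10% v 20% is a test for a difference, not the equivalence test that C.1 plans.

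**The plan states a Bonferroni correction**, both for identifying confounders and for significance. The simulation applied none. This stands in part: a correction across models could bring the 7% down, but C.4 does not define the families, so it cannot be assumed to cover a choice between analyses of the same outcome.

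**Randomisation does not make adjustment wrong.** A reader might take the sentence on confounding in C.1 to show that it does. It does not: main effects cost almost nothing (SE 0.38 to 0.40). Nor does outcome screening by itself inflate type I error here.

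**C.1 does not commit to adjusting for antibiotic days.** It speaks only of handling them after the fact. For a child readmitted with the abscess, days before the first discharge precede randomisation. This stands; the point is that nothing rules out adjusting for days after drainage.

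**Conclusion.** The concern holds as a failure to fix one arm comparison on the scale of the design. The mismatch with the 10-point difference, the 31 expected events and the unranked list of analyses follow from the documents alone. The roughly 7% chance that at least one of three models is significant rests on the assumed covariates and on no multiplicity correction. It concerns false differences; the matching figure for a false claim of equivalence was not computed.

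The effect of interactions depends on choices that C.4 leaves open. Under assumed covariate distributions the arm SE rises about 1.1 to 1.3 times if covariates are centred (with the reported SE then somewhat too small), about 2.4 to 3.2 times with arm-by-age alone uncentred, and about 5 to 7 times only with all four uncentred. The last is an extreme case, not the expected result of following the plan.

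**What to change.** State in C.4:

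- **Primary comparison.** The difference in readmission proportions in all randomised children, with its confidence interval read against the 10-point margin. No outcome-screened terms, no arm-by-covariate interactions and no post-randomisation covariates. Give the interval's level: the stated sample size corresponds to two one-sided tests at 0.05, that is, a 90% interval.
- **One supportive analysis.** Adjusted for a short fixed list of values known before randomisation and reliably collected, for example age, admission WBC, and whether the abscess arose in hospital or led to readmission. Main effects only, standardised to a risk difference. Abscess size is less suitable, since C.4 expects it only when available.
- **Exploratory.** Confounder screening and interactions, with covariates centred.

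The cost is wording in C.4, with no extra patients or data. The downside is that the main result would not be adjusted, in response to the data, for a chance imbalance. The fixed supportive model largely covers that.

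### C.4 attaches a Bonferroni correction to its definition of significance without stating the family or exempting readmission, while C.1 sizes the trial at an uncorrected 0.05

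*Combined protocol and SAP*

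**What the plan says.** Section C.1 declares the design: "This research proposes a randomized, prospective, equivalence trial design to test the research hypothesis". It expects 10% readmission in both arms. On the margin it states: "The clinical difference in primary outcome between the two groups that we are prepared to accept is equal or greater than 10" percent. On size it states: "The sample size needed to attain a power of 0.80 at alpha=0.05 is 342", that is, 171 per arm with 10% allowed for attrition. It mentions no allowance for multiple testing.

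Section B names one primary outcome, readmission, and four secondary outcomes. It puts them under one central hypothesis, which "is whether a 4-day antibiotics course is equivalent to an 8-day course for post-drainage primary and secondary clinical outcomes".

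Section C.4 mentions Bonferroni twice. The first mention concerns the search for confounders and refers to families of tests without defining them. The second is the plan's only definition of significance: "Statistical significance will be defined as an alpha of 0.05, with two-sided alternative hypothesis and a Bonferroni correction for multiple comparison". Neither gives a divisor, and neither says whether the test of readmission is included. The comparisons that C.4 plans are tests of differences and odds ratios. It names no equivalence test and no confidence interval for a risk difference.

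**The concern.** A sample size holds only for the alpha at which the test is carried out. If the correction in C.4 reaches readmission, the trial is tested at a stricter level than the one it was sized for.

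The direction of the error also matters. Bonferroni guards against false claims of a difference. This trial hopes to conclude that 4 and 8 days are equivalent, so the error to guard against is missing a real difference. With difference tests, a stricter alpha makes that error more likely. Section D.1 says that the investigators would consider going further, to no antibiotic at drainage, if the study succeeds. A false finding of no difference could therefore shape the next trial.

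**Working it through.** **Inputs.** From C.1: readmission 10% in each arm, alpha 0.05, power 0.80, 171 per arm including 10% attrition. The 10-point figure in C.1 is read as the equivalence margin. From Section B: one primary and four secondary outcomes, five in all. Using five as the divisor is an assumption.

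**Step 1: reproduce the 342.** For two one-sided tests (TOST) at 0.05 each:

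n per arm = [2 × 0.10 × 0.90] × (1.645 + 1.282)² / 0.10² = 154.1, so 155.

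Adding 10%: 155 × 1.10 = 170.5, so 171 per arm and 342 in total. This matches exactly, with no correction. TOST at 0.025 per side needs 190 per arm before attrition. A two-sided difference test of 10% versus 20% needs 199. A one-sided difference test of 10% versus 20% needs 157 (173 with 10% added), which is close but does not fit an equivalence design.

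**Step 2: equivalence power after correction.** With no true difference, power = 2Φ(0.10/SE − z) − 1, where SE = √(0.18/n). At n = 155, SE = 0.0341 and 0.10/SE = 2.934. At n = 171, SE = 0.0324 and 0.10/SE = 3.082.

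| Level per side | z | Power, 155 per arm | Power, 171 per arm |
|---|---|---|---|
| 0.05 (as sized) | 1.645 | 80.3% | 84.9% |
| 0.025 (halved, no Bonferroni) | 1.960 | 67.0% | 73.8% |
| 0.01 (0.05/5) | 2.326 | 45.7% | 55.0% |
| 0.005 (halved, then /5) | 2.576 | 28.0% | 38.7% |

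Exact binomial enumeration at 155 per arm gives 80.5%, 46.5% and 30.2% at 0.05, 0.01 and 0.005 per side.

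Other divisors at 0.05/k per side, 155 per arm: k = 2, 67.0%; k = 3, 58.0%; k = 4, 51.2%; k = 10, 28.0%.

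**Step 3: size needed to keep 80% with k = 5.** At 0.01 per side: 0.18 × (2.326 + 1.282)² / 0.01 = 234.3, so 235 per arm before attrition. At 0.005 per side the same formula gives 268.

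**Step 4: the difference test that C.4 plans.** Take true readmission of 10% versus 20%, a difference equal to the margin, with 155 per arm and a pooled two-sided z-test. The null SE is √(2 × 0.15 × 0.85/155) = 0.0406 and the alternative SE is √((0.09 + 0.16)/155) = 0.0402.

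- Alpha 0.05: power = Φ((0.10 − 1.960 × 0.0406)/0.0402) = 69.5%, so non-significance is 30.5% (29.7% by exact enumeration).
- Alpha 0.01: power = Φ((0.10 − 2.576 × 0.0406)/0.0402) = 45.6%, so non-significance is 54.4% (the same by exact enumeration).

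**The case against.** A reader might infer that C.4 corrects every significance claim and that power therefore falls to 28–46%. The documents do not support that as a flat statement, for four reasons.

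- The correction is described as being for multiple comparison, and a single primary test is not one. On that ordinary reading readmission stays at 0.05 and no power is lost.
- The family of five is inferred. The abstract lists three secondary outcomes, Section B four, and C.4 a different four. If Section B means that equivalence must hold on all outcomes jointly, no division of alpha is needed.
- The 28% is not due to Bonferroni alone. It also halves the per-side level used in the sizing, a step that by itself lowers power to 67% at 155 per arm.
- The 155 assumes that the full 10% is lost. C.1 elsewhere expects little attrition, and with all 171 evaluable the two figures are 55% and 39%.

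It is also true that the power loss belongs to an equivalence test that C.4 never names, and that reading non-significance as equivalence carries a 30% error in Step 4 with no correction at all.

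All of this stands, and it makes the power figures conditional. It does not settle which reading applies. The general sentence on significance contains no exemption, and it would add little if Bonferroni were meant only for the confounder screens. Nor does it remove the second problem: whichever outcomes are corrected, C.4 applies the correction to difference tests of outcomes that the trial hopes to call equivalent.

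**Conclusion.** The concern holds in conditional form. C.4 leaves open whether readmission is corrected and over how many tests, and C.1 made no allowance for a correction.

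- **Readmission exempt:** the stated 80% stands, for TOST at 0.05 per side.
- **Readmission corrected:** the 80% is lost, even with a divisor of two (67% at 155 per arm). With an assumed family of five it is about 46% at 0.01 per side (55% if all 171 are evaluable), and about 28% (39%) if the per-side level is also halved.
- **Either way:** correcting a difference test favours a finding of no difference. If readmission is corrected over five tests, a true 10% versus 20% is missed in about 54% of trials rather than 30%. If it is exempt, the same effect falls on the secondary outcomes.

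These figures rest on 10% readmission in both arms for the equivalence power, a 10-point margin, and the assumed divisor. Because one sentence yields either 80% or much less for the primary conclusion, the threshold should be fixed before any data are compared.

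**What to change.** Replace the significance sentence in C.4 with a statement to this effect:

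- Readmission is the single primary outcome and is tested without Bonferroni correction.
- Equivalence is tested by two one-sided tests at 0.05 each. Equivalently, the 90% confidence interval for the risk difference must lie wholly within ±10 percentage points. This is the analysis that reproduces the 342.
- Secondary outcomes are reported as estimates with 95% confidence intervals.
- Non-significance, corrected or not, is not read as equivalence.
- Bonferroni is limited to the exploratory confounder screens.

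Naming the test and its per-side level is essential. Merely exempting readmission at 0.05 would still allow a plain difference test, or TOST at 0.025 per side with 67% power at 155 per arm.

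The change costs one paragraph and no extra patients. Its downside is that secondary outcomes become supportive rather than confirmatory, so the central hypothesis in Section B should be reworded to match. The plan states a margin only for the primary outcome, so it does not support confirmatory equivalence claims on the others in any case. Keeping readmission inside a five-test correction would instead mean re-sizing to 235 per arm before attrition at 0.01 per side, or 268 at 0.005.
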